Once we receive participants' GC, CT, and syphilis test results back from CVRL (approximately 2 weeks after they return their specimens), they will be contacted to schedule a 30 min post-test session to be conducted over Zoom with the same interventionist who conducted the pre-test session, whenever possible. Time slots will be offered in all US time zones and be flexible to meet their individual circumstances. If participants do not schedule a session within 1 week, up to 7 reminders will be sent at regular intervals over the next 7 weeks. The reminders will inform participants that not scheduling a session by the end of 8 weeks suggests that they are no longer interested (unless they request an extension). Once a time is confirmed, participants will be sent a password-protected Zoom link. They will be advised to join the session from a private location and be offered the option to reschedule if the original time no longer works or if they anticipate being in a situation where their privacy may be compromised.

Post-test sessions will be conducted from a private location and participants will have the option to mute their own video (i.e., use only audio from their end) if they prefer to remain discreet. Sessions will be audio-recorded using a digital voice recorder to allow for the ongoing monitoring of intervention fidelity. No audio or video will be recorded in Zoom. The audio recordings will be transferred to a secure UM server immediately after the session, and then deleted from the digital voice recorder. The recordings will not be transcribed, but IRB-approved study team members will listen to them on an ongoing basis to identify and discuss areas of potential improvement. The recordings will be deleted from the UM server upon study completion (i.e., when all study-related data have been collected and checked for accuracy and completeness). During the session, the interventionist will follow procedures described in the post-test intervention outline. The session will incorporate the four MI processes of *Engaging*, *Focusing*, *Evoking*, and *Planning*. It will begin with a conversation to initiate a collaborative partnership and build rapport. The

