
For participants receiving a positive GC, CT, or syphilis test result, a study team member will review their state and local statutory reporting requirements and procedures and make up to 3 attempts to notify the relevant public health authorities. Reporting of these bacterial STIs can be performed without providing isolates. Participants' contact information will be reported. This notification may result in participants being contacted by their public health authorities for follow up and possible contact tracing. A study team member will also follow up via phone at 2 weeks and at 4 weeks to determine their treatment status. During each of these interactions, the study team member will complete a case report form programmed in Qualtrics documenting whether the participant has initiated treatment, completed treatment, has not yet initiated treatment but has made an appointment with a provider, or has not yet made an appointment with a provider. Those who have not yet made an appointment with a provider will be encouraged to do so as soon as possible and offered additional assistance as requested. The data entered into the case report forms will be downloaded to a secure UM server.

Participants who do not schedule or attend the post-test session will be deemed not interested in this intervention component (unless they have contacted us to reschedule). However, a copy of the lab test results form and the supplemental information sheet on using site locators to identify local STI clinics will be shared with these participants via a secure Dropbox folder that is only accessible to them and the study team members. The link to the folder will expire after 4 weeks and the folder will be deleted, following which participants will need to contact us to obtain a new link.

Note: Qualtrics, Zoom, and Dropbox are approved by the UM ITS for sensitive identifiable human subjects research data regulated by the "Common Rule". Access to the Qualtrics, Zoom, and Dropbox accounts is protected with a sufficiently complex password and requires Duo two-factor authentication for login. Only IRB-approved study team members, all of whom will have completed trainings on human subjects research protections offered by the UM PEERRS, will have access to participants' data on an as-needed basis.

e. Satisfaction survey

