- (ix) Likelihood of testing for bacterial STIs in the future: 5-point Likert items to assess the participant's likelihood of testing for bacterial STIs at least annually and likelihood of using home STI tests sold online by companies.

The satisfaction survey should take approximately 30 min to complete, and it will allow participants to skip questions or indicate that they prefer not to answer a question. If participants do not complete the satisfaction survey within 1 week, up to 7 reminders will be sent at regular intervals over the next 7 weeks. The reminders will inform participants that non-completion of the satisfaction survey by the end of 8 weeks suggests that they are no longer interested (unless they request an extension). Those who complete the satisfaction survey will receive a \$20 Amazon egift card.

Note: Qualtrics is approved by the UM ITS for sensitive identifiable human subjects research data regulated by the "Common Rule". Access to the Qualtrics account is protected with a sufficiently complex password and requires Duo two-factor authentication for login. The data collected via the satisfaction survey will be downloaded to a secure UM server. Only IRB-approved study team members, all of whom will have completed trainings on human subjects research protections offered by the UM PEERRS, will have access to participants' data on an as-needed basis.

Section 4. Phase 2 procedures

To gain a deeper understanding of attitudes, facilitators, and barriers related to engaging in each component of the intervention, we will conduct in-depth interviews with a subsample of 20 participants. Purposive sampling will be used to select a mix of participants who complete progressively smaller subsets of the pre-test session, specimen return for bacterial STI testing, and the post-test session. 108

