Protections to safeguard participants who test positive for one or more bacterial STIs and link them to medical care: For participants receiving a positive GC, CT, or syphilis test result, the interventionist will offer emotional support, discuss the benefits of timely antibiotic treatment, and jointly formulate a linkage to care plan during the post-test session to be conducted over Zoom. Barriers to accessing treatment (e.g., lack of insurance, limited personal transportation, reluctance to visit one's own provider) will be elicited and the interventionist will work with participants to find practical solutions. For example, if someone lacks insurance, screen sharing will be used to give information on local STI clinics that provide free or low-cost services identified using site locators on the CDC's "GetTested: National HIV, STD, and Hepatitis Testing" and Planned Parenthood's "STD Testing, Treatment & Vaccines" websites. If someone has limited personal transportation, the interventionist will assist in creating a commute plan that uses public transportation options. If someone is reluctant to visit their own provider, the interventionist will assist in finding other STI clinics or identifying commercial telehealth services that offer STI treatment (e.g., GoodMDs, PlushHealth, CallonDoc). Participants will be encouraged to notify their sex partners of their positive test results so that they can seek testing. Open-ended questioning and reflective listening will be used to engage them in a discussion on sexual risk reduction. A study team member will follow up via phone at 2 weeks and at 4 weeks to determine participants' treatment status. During each of these interactions, the study team member will complete a case report form programmed in Qualtrics documenting whether the participant has initiated treatment, completed treatment, has not yet initiated treatment but has made an appointment with a provider, or has not yet made an appointment with a provider. Those who have not yet made an appointment with a provider will be encouraged to do so as soon as possible and offered additional assistance as requested.

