Protections to safeguard confidentiality: To minimize risks to confidentiality, we will provide all of the appropriate protections to participants' data collected as part of our study. UM has signed Business Associate Agreements with Qualtrics, Zoom, and Dropbox. These resources are approved by the UM ITS for sensitive identifiable human subjects research data regulated by the "Common Rule". Access to the Qualtrics, Zoom, and Dropbox accounts is protected with a sufficiently complex password and requires Duo two-factor authentication for login. Duo protects applications by using a second source of validation, like a phone or token, to verify user identity before granting access. Individuals whose contact information has been verified will be assigned a randomly generated participant ID number to be included as a metadata element in subsequent baseline and satisfaction surveys programmed in Qualtrics. Participants' contact information (full name, email address, mobile phone number, and mailing address) will be kept separate from the quantitative and qualitative data collected during Phases 1 and 2 of our study in a passwordprotected file stored on a secure UM server. Only IRB-approved study team members, all of whom will have completed trainings on human subjects research protections offered by the UM PEERRS, will have access to participants' data on an as-needed basis. Any specimens returned by participants within 8 weeks will be destroyed immediately after lab testing. Any specimens returned after 8 weeks will be destroyed without being tested (unless they are from participants who have requested an extension). Lab personnel at CVRL or EML will only be able to connect the participants' test results to the unique specimen ID numbers affixed to the different transport tubes. They will not have access to either the participant ID numbers or to the participants' contact information. Only IRB-approved study team members at the UM will have access to the data on which unique specimen ID numbers are assigned to a particular participant ID number, and which participant ID number corresponds to a particular participant's contact information. The data collected via the eligibility screener, contact information form, baseline survey, case report form, and satisfaction survey will be deleted from Qualtrics upon study completion (i.e., when all studyrelated data have been collected and checked for accuracy and completeness). The audio recordings from our pre-test sessions, post-test sessions, and in-depth interviews will be deleted from the UM server upon study completion (i.e., when all study-related data have been collected and checked for accuracy and completeness). The file containing participants' contact information will also be deleted from the UM server upon study completion (i.e., when all study-related data have been collected and checked for accuracy and completeness). All other data collected as part of our study (i.e., survey responses, case report form data, in-depth interview transcripts) will be stored on a secure UM server for subsequent analyses and reporting, and the only link between them will be the participant ID numbers (i.e., none of the files will contain any sort of personally identifiable information except ZIP code). Results from our study will be described in a manner such that no individual participants can be identified. Our study is funded by the NIH and holds a Certificate of Confidentiality.

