- (iii) Improvement in self-efficacy for specimen self-collection: Potential increases in participants' self-efficacy for urine sample self-collection, throat swab self-collection, rectal swab self-collection, and finger-stick blood sample self-collection will be assessed by comparing responses to similar sets of four 5-point Likert items included in the baseline survey and the satisfaction survey. Response values will be summed to obtain separate total scores ranging from 4-20, with higher scores indicating greater self-efficacy for specimen self-collection.

Outcomes to measure the prevalence of bacterial STIs and receipt of treatment include the following:

- (i) Number of participants that test negative or positive for GC, CT, and syphilis (using our specimen self-collection kits or with their own provider or at a clinic).
- (ii) Number of participants that initiate treatment (with their own provider or at a clinic or via commercial telehealth services) within 1 week of receiving a positive test result.

Because our study is inherently exploratory, we do not plan on using probability-based statistical inference techniques in line with current best practices. ^{109, 110} Instead, potential variations in our intervention's feasibility and acceptability across selected participant characteristics, and its potential impact on IMB model constructs will be numerically summarized and graphically visualized (e.g., side-by-side boxplots, scatter plots), as recommended for exploratory data. ^{111, 112}

Ame00145753

Instead of using a bubble mailer for participants to return their specimens, we will be using a shipping box made of cardboard as the outer shipping package. This change is to promote compliance with the Hazardous Materials Regulations for the safe transportation of hazardous materials, including Category B infectious substances, that recommend the use of "rigid outer packaging" (HMR; 49 CFR §173.199). To reflect this change, we have replaced the phrase "bubble mailer" with "shipping box" in the informed consent form and have updated the general information sheet that includes packaging instructions for participants. We have also included our contact details in the general information sheet and the supplemental information sheet so that

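### The treatment outcome counts starts within 1 week of a positive result, but the follow-up described records only a status at 2 and 4 weeks, with no start date

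*Combined protocol and SAP*

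**What the plan says.** Ame00143150 replaces the outcome list in Section 5.a. Under secondary outcomes, the second item on prevalence and treatment counts participants who start treatment with their own provider, at a clinic, "or via commercial telehealth services) within 1 week of receiving a positive test result". The item before it counts negative and positive tests obtained "using our specimen self-collection kits or with their own provider or at a clinic", so positives found outside the study are also in scope.

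Treatment status is collected as set out in Section 3.d: "A study team member will also follow up via phone at 2 weeks and at 4 weeks to determine their treatment status". At each call a case report form is completed, "documenting whether the participant has initiated treatment, completed treatment, has not yet initiated treatment but has made an appointment with a provider"; the fourth category is that no appointment has been made. Section 6.b repeats the arrangement: "A study team member will follow up via phone at 2 weeks and at 4 weeks".

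Positive results reach participants in one of two ways (Section 3.d). Those who attend the post-test session see them on a shared screen. Those who do not schedule or attend it are given access to a Dropbox folder.

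Section 5.a in the body of the protocol, which the amendment supersedes, used windows of 2 and 4 weeks.

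**The concern.** The outcome needs the time from receipt of a positive result to the start of treatment, at least to the precision of before or after day 7. The follow-up described gives a status on two occasions, both later than day 7, and no date. The superseded windows coincided with the calls. The amended window does not, and no amendment shown changes the calls or the form.

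This is the only treatment outcome in the amended list. If the data are collected as described, the team will have to report a range, or treat everyone who has started by the 2-week call as having started within 1 week, which gives the upper limit as though it were the count. The gap would be hard to repair afterwards, because Section 6.b has the contact-information file deleted at study completion, after which missing dates could not be sought.

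**Working it through.** **1. Which text is operative.** Ame00143150 presents its list as the amended text of Section 5.a. The body has not been updated for the amendments: Section 1.b there lacks the sentences that Ame00143150 adds, and Section 3.c still describes the return packaging that Ame00145753 replaces. The 1-week outcome is therefore current. The point does not rest on its differing from the superseded text, but on its having no matching data source.

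**2. Whether another source holds the date.** Section 6.b, on confidentiality, names the Qualtrics instruments: "The data collected via the eligibility screener, contact information form, baseline survey, case report form, and satisfaction survey will be deleted from Qualtrics". Taking these in turn, with the interviews:

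- The eligibility screener, contact form and baseline survey come before the results. The baseline item on treatment concerns past history.
- The satisfaction survey (Section 3.e) has nine topics, ending with "Likelihood of testing for bacterial STIs in the future: 5-point Likert items". None is treatment received.
- The Phase 2 interviews cover 20 participants and concern engagement with the intervention components.
- That leaves the case report form, described only by its four statuses.

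**3. What the calls can distinguish.** Assume that the calls fall on days 14 and 28 after receipt of the result and that answers are accurate. Let *s* be the day treatment starts. Started means recorded as initiated or completed.

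| Start day *s* | 2-week call | 4-week call | Within 1 week? |
|---|---|---|---|
| 0–14 | started | started | cannot be told |
| 15–28 | not started | started | no |
| after 28 | not started | not started | no |
| 0–28 | missed | started | cannot be told |
| after 28 | missed | not started | no |

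Day 7 lies inside the first interval, so starts on day 3 and day 12 give the same record. The 4-week call does not separate them.

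**4. The resulting limits.** Let *I2* be the number recorded as started at the 2-week call. Let *M* be the number of positive participants who missed that call and were not recorded as un-started at the 4-week call. Let *k* be the number with a positive result. Then

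0 ≤ 1-week count ≤ *I2* + *M*.

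With all 2-week calls completed, *M* = 0 and the range is 0 to *I2*, or 0 to *I2*/*k* as a proportion. It is a single value only if *I2* + *M* = 0. Each further participant counted in *M* raises the upper limit by 1. The documents give no expected positivity or initiation rate, so the width cannot be put as a percentage.

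**5. The start point.** Sections 3.d and 6.b do not say what the 2 and 4 weeks are counted from. Scheduling of the post-test session may take 1 week plus 7 weeks of reminders, that is 8 weeks, after the team contacts the participant: "The reminders will inform participants that not scheduling a session by the end of 8 weeks suggests that they are no longer interested", unless an extension is requested. If the calls were counted from when the team has the results, and the participant received them *d* days later, the 2-week call would fall on day 14 − *d* after receipt. Once *d* exceeds 7, that call precedes day 7, and even a not-started status at that call would not settle the outcome. No procedure for a missed treatment call is described; the limit of three attempts in Section 3.d concerns notifying public health authorities.

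**The case against.** The strongest objection is that the case report form is not in the documents. Sections 3.d and 6.b summarise it in a clause, and a date field is neither described nor excluded. The lists used in step 2 are also not complete: Ame00147802 adds a re-consent survey that Section 6.b does not list, and the superseded Section 5.a plans a comparison with the last testing experience that is not among the satisfaction-survey topics. Absence from a list is therefore weak evidence that an item is not collected. This stands, and it limits the conclusion to the follow-up described. It does not remove the need for the plan to say where the date comes from.

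A second objection is that receipt of the result is the natural start point, since Section 3.d introduces the calls for participants receiving a positive result and the superseded Section 5.a counts its windows from receipt. For those who attend the session, the 8-week scheduling period then ends before the clock starts. This is largely right. Real uncertainty remains for those who receive results by folder, where no record of opening is described, and for results obtained outside the study. The start point and missed calls are secondary to the main mismatch.

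Third, this is one descriptive count in an exploratory pilot of 75, with no inference planned, and it applies only to those who test positive. That is also right. The completed calls still give an upper limit, and the 2-week and 4-week statuses can still be reported.

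**Conclusion.** The concern holds. From the follow-up described, the number starting treatment within 1 week cannot be derived. It is known only to lie between 0 and the number started by the 2-week call, plus any participants missed at that call who are not shown at 4 weeks to be un-started. This assumes calls timed from receipt of the result, accurate answers, and no start date on the unreproduced form. If the form does hold a start date, the main gap is one of description only.

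The consequence is confined to one secondary outcome. It should be fixed, because it is the only treatment outcome in the amended list and the remedy is small.

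**What to change.** If the case report form already records a start date, say so in Sections 3.d and 5.a. If not, one of two changes will do.

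- **Add dates.** Put the date treatment started and the date the positive result was received on the form used at the existing calls. For study-kit results, take the post-test session date as receipt, or the folder-share date as a stated approximation for those who miss the session. For results from a participant's own provider or a clinic, take the self-reported date, or limit the outcome to study-kit positives. The cost is two fields and a sentence each in Sections 3.d, 5.a and 6.b, with no extra contact. Self-reported dates carry modest recall error, and the folder-share date only approximates receipt.
- **Change the window.** Report initiation by the 2-week and 4-week calls. This needs no new data, but it does need a protocol amendment. Ame00143150 says that the amended outcomes agree with ClinicalTrials.gov, so the registry entry may also need updating; that entry was not available to check.

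Either way, state what the 2 and 4 weeks are counted from and how missed calls are handled, and report the count beside the number testing positive. Sections 3.d, 5.a and 6.b must be reconciled. Both options concern data collection and reporting only.
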